10.4 Evaluation of Response

To determine time point response, refer to **Table 6**, and **Table 7** below.

Table 6 Time Point Response Criteria (+/- non-target disease)

Target Lesions	Non-Target Lesions ¹	New Lesions ¹	Overall Response
CR	CR	No	CR
CR	Non-CR/Non-PD	No	PR
CR	Not evaluated	No	PR
PR	Non-PD or not all evaluated	No	PR
SD	Non-PD or not all evaluated	No	SD
Not all evaluated	Non-PD	No	NE
PD	Any	Yes or No	PD ¹
Any	PD ¹	Yes or No	PD ¹
Any	Any	Yes	PD ¹

Table 7 Time Point Response Criteria (non-target disease only)

Non-Target Lesions ¹	New Lesions ¹	Overall Response
CR	No	CR
Non-CR/non-PD	No	Non-CR/non-PD ¹
Not all evaluated	No	NE
Unequivocal PD	Yes or No	PD ¹
Any	Yes	PD ¹

¹ If new or worsening lesions are found in the brain only, these are not considered disease progression for the purposes of this study. Non-CR/non-PD is preferred over SD for non-target disease since SD is used as endpoint for assessment of efficacy in trials so to assign this category when no lesions can be measured is not advised.

The best overall response is the best response recorded from the start of study treatment until the tumor assessment obtained upon completion of nintedanib/placebo treatment taking into account any requirement for confirmation. In general, the participant’s best response assignment will depend on the achievement of both measurement and confirmation criteria and will be determined by combining the participant’s status of target lesions, non-target lesions, and new lesions.

- **Residual Disease:** Provide the appropriate information that pertains to this study.
- **Symptomatic Deterioration:** Participants with global deterioration of health status requiring discontinuation of treatment without objective evidence of disease progression at that time, and not related to study treatment or other medical conditions should be reported as progressive disease due to “symptomatic deterioration.” Every effort should be made to document objective progression even after discontinuation of treatment due to symptomatic deterioration. Symptomatic deterioration that may lead to discontinuation of treatment include, but is not limited to, symptoms such as:
 - Weight loss > 10% of body weight.
 - Worsening of disease-related symptoms (e.g., worsening dyspnea, increasing pain/increasing requirement for narcotic analgesics).
 - Decline in performance status of > 1 level on ECOG scale.

10.5 Confirmation Measurement

To be obtained as clinically warranted in cases of suspected tumor progression.

10.6 Guidelines for Evaluation of Measurable Disease

All measurements should be taken and recorded in metric notation using a ruler or calipers. All baseline evaluations should be performed as closely as possible to the beginning of treatment and never more than 4 weeks before the beginning of the treatment.

The same method of assessment and the same technique should be used to characterize each identified and reported lesion at baseline and during follow-up. Imaging-based evaluation is

preferred to evaluation by clinical examination unless the lesion(s) being followed cannot be imaged but are assessable by clinical exam.

- **Clinical Lesions:** Clinical lesions will only be considered measurable when they are superficial (e.g., skin nodules and palpable lymph nodes) and ≥ 10 mm diameter as assessed using calipers (e.g., skin nodules). In the case of skin lesions, documentation by color photography, including a ruler to estimate the size of the lesion, is recommended.
- **Chest x-ray:** Lesions on chest x-ray are acceptable as measurable lesions when they are clearly defined and surrounded by aerated lung. However, CT is preferable.
- **Conventional CT and MRI:** This guideline has defined measurability of lesions on CT scan based on the assumption that CT slice thickness is 5 mm or less. If CT scans have slice thickness greater than 5 mm, the minimum size for a measurable lesion should be twice the slice thickness. MRI is also acceptable in certain situations (e.g., for body scans).

Use of MRI remains a complex issue. MRI has excellent contrast, spatial, and temporal resolution; however, there are many image acquisition variables involved in MRI, which greatly impact image quality, lesion conspicuity, and measurement. Furthermore, the availability of MRI is variable globally. As with CT, if an MRI is performed, the technical specifications of the scanning sequences used should be optimized for the evaluation of the type and site of disease. Furthermore, as with CT, the modality used at follow-up should be the same as was used at baseline and the lesions should be measured/assessed on the same pulse sequence. It is beyond the scope of the RECIST guidelines to prescribe specific MRI pulse sequence parameters for all scanners, body parts, and diseases. Ideally, the same type of scanner should be used and the image acquisition protocol should be followed as closely as possible to prior scans. Body scans should be performed with breath-hold scanning techniques, if possible.

- **PET-CT:** At present, the low dose or attenuation correction CT portion of a combined PET-CT is not always of optimal diagnostic CT quality for use with RECIST measurements. However, if the site can document that the CT performed as part of a PET-CT is of identical diagnostic quality to a diagnostic CT (with IV and oral contrast), then the CT portion of the PET-CT can be used for RECIST measurements and can be used interchangeably with conventional CT in accurately measuring cancer lesions over time. Note, however, that the PET portion of the CT introduces additional data which may bias an investigator if it is not routinely or serially performed.
- **Ultrasound:** Ultrasound is not useful in assessment of lesion size and should not be used as a method of measurement. Ultrasound examinations cannot be reproduced in their entirety for independent review at a later date and, because they are operator dependent, it cannot be guaranteed that the same technique and measurements will be taken from one assessment to the next. If new lesions are identified by ultrasound in the course of the study, confirmation by CT or MRI is advised. If there is concern about radiation exposure at CT, MRI may be used instead of CT in selected instances.
- **Endoscopy, Laparoscopy:** The utilization of these techniques for objective tumor evaluation is not advised. However, such techniques may be useful to confirm complete

pathological response when biopsies are obtained or to determine relapse in trials where recurrence following complete response (CR) or surgical resection is an endpoint.

- **Tumor Markers:** Tumor markers alone cannot be used to assess response. If markers are initially above the upper normal limit, they must normalize for a participant to be considered in complete clinical response.
- **Cytology, Histology:** These techniques can be used to differentiate between partial responses (PR) and complete responses (CR) in rare cases (e.g., residual lesions in tumor types, such as germ cell tumors, where known residual benign tumors can remain).

The cytological confirmation of the neoplastic origin of any effusion that appears or worsens during treatment when the measurable tumor has met criteria for response or stable disease is mandatory to differentiate between response or stable disease (an effusion may be a side effect of the treatment) and progressive disease.

- **FDG-PET:** While FDG-PET response assessments need additional study, it is sometimes reasonable to incorporate the use of FDG-PET scanning to complement CT scanning in assessment of progression (particularly possible 'new' disease). New lesions on the basis of FDG PET imaging can be identified according to the following algorithm:
- Negative FDG-PET at baseline, with a positive FDG-PET at follow-up is a sign of PD based on a new lesion.
- No FDG-PET at baseline and a positive FDG-PET at follow-up: If the positive FDG-PET at follow-up corresponds to a new site of disease confirmed by CT, this is PD. If the positive FDG-PET at follow-up is not confirmed as a new site of disease on CT, additional follow-up CT scans are needed to determine if there is truly progression occurring at that site (if so, the date of PD will be the date of the initial abnormal FDG-PET scan). If the positive FDG-PET at follow-up corresponds to a pre-existing site of disease on CT that is not progressing on the basis of the anatomic images, this is not PD.
- FDG-PET may be used to upgrade a response to a CR in a manner similar to a biopsy in cases where a residual radiographic abnormality is thought to represent fibrosis or scarring. The use of FDG-PET in this circumstance should be prospectively described in the protocol and supported by disease-specific medical literature for the indication. However, it must be acknowledged that both approaches may lead to false positive CR due to limitations of FDG-PET and biopsy resolution/sensitivity.

Note: A 'positive' FDG-PET scan lesion means one which is FDG avid with an uptake greater than twice that of the surrounding tissue on the attenuation corrected image.

10.7 Radiation Pneumonitis Score

Multidetector helical CT images of the chest will be obtained from the supraclavicular region to the level of adrenals with the patient in a supine position. A 5 mm slice thickness and appropriate DFOV will be applied during a single inspiratory breath hold acquisition. Post processing with a coronal and sagittal planes will be performed. IV contrast will be administered.

Images will be sent to PACS (Picture Archiving and Communications System) and viewed and analyzed on a workstation. For cases performed outside of RPCI, DICOM (Digital Imaging and

Communications in Medicine) archived images on CD disk will be sent to RPCI Radiology Department for central review.

Visual analysis will be performed by two thoracic radiologists who will independently record the pulmonary fibrosis score. The lungs will be divided into three zones. Upper zone is from the level of apex to the carina. Lower zone being inferior to the pulmonary veins. Middle zone is anywhere in between the two. Semi quantitative analysis will be performed for the presence of ground-glass opacity, consolidation, reticulation, mosaic perfusion, traction bronchiectasis and honeycombing for each lung zone and scored on a four point scale (0 = no involvement, 1 ≤ 25%; 2 = 26 - 50%; 3 = 51 - 75% and 4 ≥ 76%). A highest severity score for each of the 6 lung zones and overall highest volume of disease involvement will be calculated. Baseline, 3 month, 6 month, 9 month and 1 year follow-up HRCT images after completion of nintedanib/placebo treatment will be scored during the trial. The observers will be blinded to the treatment for the approximately 100 patients that will be recruited.

10.8 Radiation Treatment Field Central Review/Radiation Specifications (adapted from NCCN guidelines for NSCLC version 4.2014)

Central review will be performed and essential parameters such as V20 and MLD will be recorded for each patient. For treatment volume consideration for 3D-conformal RT, planning target volume should be defined using the ICRU-50 and ICRU-62 (international Commission on Radiation Units and Measurements Reports 50 and 62) reports, based on gross tumor volume (GTV), plus clinical target volume margins for microscopic diseases, internal target volume margins for target motion, and margins for daily set-up errors. ICRU Report 83 is used for IMRT. The ACR-ASTRO guidelines are also useful (<http://www.acr.org/~media/eabb986bc4ff4a78b53b001a059f27b3.pdf>). Additional volume considerations are described in the NCCN algorithm. It is essential to evaluate the dose volume histogram (DVH) of critical structures and to limit the doses to the spinal cord, lungs, heart, esophagus and brachial plexus to minimize normal tissue toxicity (Refer to Table 5 under Principles of Radiation Therapy for NSCLC, http://www.nccn.org/professionals/physician_gls/f_guidelines.asp). These limits are empirical.

Treatment planning should be based on CT scans obtained in the treatment position. Intravenous contrast CT scans are recommended for better target delineation whenever possible, especially in patients with central tumors or with nodal diseases. PET/CT is recommended for select patients (i.e., those with significant atelectasis, when IV contrast is contraindicated). PET/CT can significantly improve the target accuracy. Whenever feasible, respiratory motion should be managed. Acceptable methods of accounting for tumor motion, per the AAPM Task Group 76 guideline, are described in the Principles of Radiation Therapy of the NCCN NSCLC algorithm. The algorithm also provides recommendations for patients receiving chemoradiation, photon beams or IMRT.

11 SAFETY EVALUATION

11.1 Adverse Events

11.1.1 Definition

An adverse event or adverse experience (AE) is any untoward medical occurrence associated with the use of a drug in humans, whether or not considered drug related. Therefore, an AE can be ANY unfavorable and unintended sign (including an abnormal laboratory finding), symptom, or disease temporally associated with the use of a medicinal (investigational) product, whether or not considered related to the medicinal (investigational) product (attribution of ‘unrelated’, ‘unlikely’, ‘possible’, ‘probable’, or ‘definite’). To capture binary classifications in the CRF, attributions of possible, probable or definite will fall under the “YES” category while attributions of unlikely and unrelated will fall under the “NO” category.

An AE is considered “unexpected” if it is not listed in the investigator brochure or is not listed at the specificity or severity that has been observed; or if an investigator brochure is not required or available, is not consistent with the risk information described in the general investigational plan in other study-related documents.

11.1.1.1 Diagnosis Versus Signs and Symptoms

If known, a diagnosis should be recorded on the CRF rather than individual signs and symptoms (e.g., record only liver failure or hepatitis rather than jaundice, asterix, and elevated transaminases). However, if a constellation of signs and/or symptoms cannot be clinically characterized as a single diagnosis or syndrome at the time of reporting, each individual event should be recorded as an AE or SAE on the CRF. If a diagnosis is subsequently established, it should be reported as follow-up information.

11.1.1.2 Adverse Events Occurring Secondary to Other Events

In general, AEs occurring secondary to other events (e.g., cascade events or clinical sequelae) should be identified by their primary cause. For example, if severe diarrhea is known to have resulted in dehydration, it is sufficient to record only diarrhea as an AE or SAE on the CRF.

However, clinically significant AEs occurring secondary to an initiating event that are separated in time should be recorded as independent events on the CRF. For example, if a severe gastrointestinal hemorrhage leads to renal failure, both events should be recorded separately on the CRF.

11.1.1.3 Abnormal Laboratory Values

Only clinically significant laboratory abnormalities that require active management will be recorded as AEs or SAEs on the CRF (e.g., abnormalities that require study drug dose modification, discontinuation of study treatment, more frequent follow-up assessments, further diagnostic investigation, etc.).

If the clinically significant laboratory abnormality is a sign of a disease or syndrome (e.g., alkaline phosphatase and bilirubin 5 x the upper limit of normal associated with cholecystitis), only the diagnosis (e.g., cholecystitis) needs to be recorded on the Adverse Event CRF.

If the clinically significant laboratory abnormality is not a sign of a disease or syndrome, the abnormality itself should be recorded as an AE or SAE on the CRF. If the laboratory abnormality can be characterized by a precise clinical term, the clinical term should be recorded as the AE or SAE. For example, an elevated serum potassium level of 7 mEq/L should be recorded as “hyperkalemia”

Observations of the same clinically significant laboratory abnormality from visit to visit should not be repeatedly recorded as AEs or SAEs on the CRF, unless their severity, seriousness, or etiology changes.

11.1.1.4 Preexisting Medical Conditions (Baseline Conditions)

A preexisting medical condition should be recorded as an AE or SAE only if the frequency, severity, or character of the condition worsens during the study. When recording such events on an Adverse Event CRF, it is important to convey the concept that the preexisting condition has changed by including applicable descriptors (e.g., “more frequent headaches”).

11.1.2 Grading and Relationship to Drug

The descriptions and grading scales found in the CTEP Version 4 of the NCI Common Terminology Criteria for Adverse Events (CTCAE) will be utilized for AE reporting. CTEP Version 4 of the CTCAE is identified and located at:

http://ctep.cancer.gov/protocolDevelopment/electronic_applications/ctc.htm.

AEs not covered by specific terminology listed should be reported with common medical terminology, and documented according to the grading scales provided in the CTCAE Version 4.

The relationship of event to study drug will be documented by the Investigator as follows:

- **Unrelated:** The event is clearly related to other factors such as the participant’s clinical state, other therapeutic interventions or concomitant drugs administered to the participant.
- **Unlikely:** The event is doubtfully related to investigational agent(s). The event was most likely related to other factors such as the participant’s clinical state, other therapeutic interventions, or concomitant drugs.
- **Possible:** The event follows a reasonable temporal sequence from the time of drug administration, but could have been produced by other factors such as the participant’s clinical state, other therapeutic interventions or concomitant drugs.
- **Probable:** The event follows a reasonable temporal sequence from the time of drug administration, and follows a known response pattern to the study drug. The event cannot be reasonably explained by other factors such as the participant’s clinical state, therapeutic interventions or concomitant drugs.

- **Definite:** The event follows a reasonable temporal sequence from the time of drug administration, follows a known response pattern to the study drug, cannot be reasonably explained by other factors such as the participant’s condition, therapeutic interventions or concomitant drugs; AND occurs immediately following study drug administration, improves upon stopping the drug, or reappears on re-exposure.

11.1.3 Reporting Adverse Events

Table 8 Guidelines for Routine Adverse Event Reporting for Phase 1 Studies (Regardless of Expectedness)

Table 9 Guidelines for Routine Adverse Event Reporting for Phase 1 Studies (Regardless of Expectedness)Attribution	Grade 1	Grade 2	Grade 3	Grade 4
Unrelated	X	X	X	X
Unlikely	X	X	X	X
Possible	X	X	X	X
Probable	X	X	X	X
Definite	X	X	X	X

Table 10 Guidelines for Routine Adverse Event Reporting for Phase 2 Studies (Regardless of Expectedness)

Attribution	Grade 1	Grade 2	Grade 3	Grade 4
Unrelated			X	X
Unlikely			X	X
Possible	X	X	X	X
Probable	X	X	X	X
Definite	X	X	X	X

Routine AEs occurring between the start date of intervention until 30 days after the last intervention or until the event has resolved, the study participant is lost to follow-up, the start of a new treatment, or until the study investigator assesses the event(s) as stable or irreversible, will be reported. New information will be reported after it is received.

Worsening of the underlying disease or of other pre-existing conditions will be recorded as an AE in the CRF.

Changes in vital signs, physical examination and laboratory test results will be recorded as an AE in the CRF, if they are judged clinically relevant by the investigator.

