- QOL Questionnaire (Cycle 3 and Cycle 6 only) (Appendix F)
- ECOG Performance Status (Appendix C)
- Tumor/Disease Assessment (Cycle 3 and Cycle 6 only)
- Dispense nintedanib/Placebo
- Concomitant Medications
- Adverse Events

9.5 Evaluations Performed Anytime When Radiation Pneumonitis is Suspected to Have Occurred (Within the First 6 Months After Completing Radiation Therapy)

- Medical history
- Physical examination, including vital signs (i.e., temperature, heart rate, respiratory rate, blood pressure, and body weight)
- Hematology [(i.e., complete blood count (CBC) with automated differentials)](or, the physicians' discretion): WBC, RBC, HGB, HCT, platelet, MCV, MCH, MCHC, % neutrophils, absolute neutrophils, % monocytes, absolute monocytes, % eosinophils, absolute eosinophils, % basophils, absolute basophils, % lymphocyte total, absolute lymphocyte total, platelet confirmation (as clinically indicated), and differential confirmation (as clinically indicated). Note: Participants experiencing Grade 4 neutropenia should be monitored according to institutional guidelines. As needed at each study visit as determined by the Investigator or study physician.
- Chemistry (i.e., complete metabolic panel (CMP): chloride, CO₂, potassium, sodium, BUN, glucose, calcium, creatinine, total protein, albumin, total bilirubin, alkaline phosphatase, AST, ALT, A/G ratio, BUN/creatinine ratio, osmol (Calc), anion gap).
- Mitochondrial DNA Assay (one 10 mL heparinized green-top tube)
- QOL Questionnaire (Appendix F)
- ECOG Performance Status (Appendix C)
- Tumor/Disease Assessment
- Concomitant Medications
- Adverse Events

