- 1 Performed within 4 weeks prior to initiation of treatment.
- 2 Follow-up to 2.5 years after completing nintedanib/placebo treatment to be conducted as part of routine/standard care. Information may be conducted by phone only if patient relocated/unable to return to treating institution(if patient unable to return, phone call follow-up includes QOL Questionnaire ([Appendix F](#)) only if possible).
- 3 Height collected at baseline only.
- 4 Hematology [(i.e., complete blood count (CBC) with automated differentials)](or, the physicians’ discretion): WBC, RBC, HGB, HCT, platelet, MCV, MCH, MCHC, % neutrophils, absolute neutrophils, % monocytes, absolute monocytes, % eosinophils, absolute eosinophils, % basophils, absolute basophils, % lymphocyte total, absolute lymphocyte total, platelet confirmation (as clinically indicated), and differential confirmation (as clinically indicated). Note: Participants experiencing Grade 4 neutropenia should be monitored according to institutional guidelines. As needed at each study visit as determined by the Investigator or study physician.
- 5 Chemistry (i.e., complete metabolic panel (CMP): chloride, CO₂, potassium, sodium, BUN, glucose, calcium, creatinine, total protein, albumin, total bilirubin, alkaline phosphatase, AST, ALT, A/G ratio, BUN/creatinine ratio, osmol (Calc), anion gap).
- 6 For routine tumor assessment, CT abdomen and pelvis with high-resolution CT chest (HRCT) should be obtained. HRCT chest alone will be sufficient whenever new onset of dyspnea occurs and radiation pneumonitis is suspected to have occurred (within the first 6 months after completing radiation therapy). CT chest obtained/configured at 1.25 mm slice thickness is an acceptable alternative to HRCT. Maximum slice thickness allowed for CT chest is 2.5 mm. Use of intravenous contrast for the CT studies is preferred but not mandatory.
- 7 To be performed prior to drug administration on Day 1 of Cycles 3 and 6 (± 7 days window) only.
- 8 Medications ongoing within 1 week prior to first dose of study drug.
- 9 Sample collection will be obtained anytime when radiation pneumonitis is suspected to have occurred (within the first 6 months after completing radiation therapy).
- 10 Urinalysis after baseline will be performed per clinical discretion / judgement.
- 11 For females of child-bearing potential.

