11.3.1 SAE reporting to Boehringer Ingelheim (BI)

Upon inclusion into a trial, the patient's condition is assessed (e.g., documentation of history / concomitant diagnoses and diseases), and relevant changes from baseline are noted subsequently.

All adverse events, serious and non-serious, occurring during the course of the clinical trial (i.e., from signing the informed consent onwards through 30 days following cessation of treatment) will be collected, documented by the investigator.

The investigator shall report all SAEs and non-serious AEs which are relevant to a reported SAEs and AESIs by fax using BI IIS SAE form to BI Unique Entry Point as detailed below in accordance with the following timelines:

- within five (5) calendar days upon receipt of initial and follow-up SAEs containing at least one fatal or immediately life-threatening event
- within ten (10) calendar days upon receipt of any other initial and follow-up SAEs

Boehringer Ingelheim Pharmaceuticals, Inc
[name]
[name]
[contact]

AND NCCN at [contact] or [contact]

For each adverse event, the investigator will provide the onset date, end date, intensity, treatment required, outcome, seriousness, and action taken with the investigational drug. The investigator will determine the relationship and expectedness with the investigational drug to all AEs as defined in the listed adverse event section of Boehringer Ingelheim's (BI's) Investigator Brochure for the Product.

The investigator does not need to actively monitor patients for adverse events once the clinical trial has ended. However, if the investigator becomes aware of an SAE(s) that occurred after the patient has completed the clinical trial (including any protocol specified follow-up period), it should be reported to BI if considered relevant by the investigator.

Investigators MUST report within 5 business days upon becoming aware, to Boehringer Ingelheim ANY Serious Adverse Events, whether or not they are considered related to the investigational agent(s)/intervention.

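### The Phase 2 adverse-event rules disagree on whether a Grade 2 radiation pneumonitis, which is a primary endpoint event, must be recorded when it is not attributed to study drug

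*Combined protocol and SAP*

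**What the plan says.** Section 13 makes the primary outcome a CTCAE-graded event, with Grade 2 as the threshold. Section 13.5 analyses it by intent-to-treat. Four sets of rules bear on how that event reaches the database.

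- **Section 11.1.3, Table 10.** The Phase 2 grid, "Table 10 Guidelines for Routine Adverse Event Reporting for Phase 2 Studies (Regardless of Expectedness)", marks Grades 3 and 4 for every attribution. It marks Grades 1 and 2 only for Possible, Probable and Definite, and leaves them blank for Unrelated and Unlikely. The Phase 1 grid beside it marks every cell. Below the grids, the time limit is "Routine AEs occurring between the start date of intervention until 30 days after the last intervention", followed by alternatives such as resolution of the event or the start of new treatment. A further sentence has no grade or attribution filter: "Changes in vital signs, physical examination and laboratory test results will be recorded as an AE in the CRF", if the investigator judges them clinically relevant.
- **Section 11.1.2.** Attribution is to study drug. Unrelated covers events due to the patient's "clinical state, other therapeutic interventions or concomitant drugs administered to the participant". Unlikely and Possible also name other therapy as an alternative cause.
- **Section 11.3.1.** "All adverse events, serious and non-serious, occurring during the course of the clinical trial", defined as "from signing the informed consent onwards through 30 days following cessation of treatment", are to be collected and documented, without a filter.
- **Sections 9.5 to 9.10 and the synopsis.** Section 9.5, "Evaluations Performed Anytime When Radiation Pneumonitis is Suspected to Have Occurred (Within the First 6 Months After Completing Radiation Therapy)", includes adverse events in its list. Table 5 marks adverse events in that column and at scheduled visits up to End of Active Treatment, and is blank at the 76-97 day, 166-187 day and long-term visits. Sections 9.7, 9.8, 9.9 and the synopsis list adverse events at all three.

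**The concern.** Grade 2 is both the lowest grade that counts as a primary event and the highest grade that Table 10 lets go unreported when the drug is not blamed. Radiation pneumonitis is by name an effect of another treatment, so an investigator could reasonably score it Unrelated or Unlikely. A site that took Table 10 as its working rule could then leave out an event that a site working from 9.5 or 11.3.1 would enter. For patients who stop early, recording inside the six-month window could also depend on whether the site follows Table 5 or the text of 9.7 to 9.9.

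Only about 16 to 17 events are expected at the planned rates, so a few unrecorded events would matter. Equal loss in both arms would cost power. Unequal loss could distort the intent-to-treat comparison.

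**Working it through.** **1. Attribution and grade.** What each rule requires for a Grade 2 pneumonitis arising on treatment:

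| Rule | Scored Unrelated or Unlikely | Scored Possible or higher |
|---|---|---|
| Table 10 | not required | required |
| 11.3.1 | required, to 30 days after treatment | required, to 30 days after treatment |
| 9.5, if pneumonitis is suspected | adverse events listed, no filter | adverse events listed, no filter |

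The gap is limited to Grade 2, because Grades 3 and 4 are marked for every attribution. It applies to completers and early stoppers alike. No passage ranks the three rules or takes pneumonitis out of Table 10.

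**2. Timing.** Inputs: first dose 4 to 8 weeks after radiation (6.2, criterion 3), so day 28 to 56; six 28-day cycles (7.5), so 168 days; a 30-day limit (11.1.3). Assumptions: six months is 183 days, counted from the end of radiation.

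- Completers: the 30-day limit ends on day 28 + 168 + 30 = 226 to day 56 + 168 + 30 = 254. Both are past day 183, so the blank Table 5 cells fall outside their endpoint window.
- Early stoppers: the limit ends before day 183 if the last dose is before treatment day 183 − 30 − 56 = 97 (start at week 8) or 183 − 30 − 28 = 125 (start at week 4).

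For that group, 11.1.3 does not clearly cover a new event after day 30, and 11.3.1 has lapsed as well. What remains is the 9.5 visit, whose clock runs from radiation, and the later visits, where Table 5 and the text disagree. History, examination, QOL and tumour assessment stay scheduled at those visits in both places.

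**3. Illustration of sensitivity.** Design inputs (13.1): 30% on placebo and 10% on nintedanib, with 33 and 66 patients. The plan's odds ratio reproduces: (0.10/0.90)/(0.30/0.70) = 0.259, stated as approximately 0.26. Expected events: 0.30 × 33 = 9.9 and 0.10 × 66 = 6.6.

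One-sided Fisher test, unstratified, because stratum sizes and the interim-adjusted critical value are not given:

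| Placebo /33 | Nintedanib /66 | p |
|---|---|---|
| 10 | 7 | 0.017 |
| 9 | 7 | 0.036 |
| 8 | 7 | 0.071 |
| 10 | 6 | 0.009 |
| 8 | 6 | 0.044 |
| 8 | 5 | 0.025 |

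One lost event does not change the conclusion. Two lost from placebo alone would. A loss of about 20% in both arms (the last two rows) would not.

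Power with an assumed equal loss in both arms, one-sided 0.05, no interim look. The normal approximation is Φ[(p₀ − p₁ − 1.645·SE₀)/SE₁], with SE₀ pooled and SE₁ unpooled. With no loss, SE₀ = √(0.1667 × 0.8333 × (1/33 + 1/66)) = 0.0795 and SE₁ = √(0.21/33 + 0.09/66) = 0.0879, so Φ[(0.20 − 0.1307)/0.0879] = 0.785.

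| Assumed loss | Recorded rates | Normal approximation | Exact Fisher |
|---|---|---|---|
| 0% | 30 vs 10% | 0.785 | 0.704 |
| 10% | 27 vs 9% | 0.741 | 0.645 |
| 20% | 24 vs 8% | 0.692 | 0.580 |
| 30% | 21 vs 7% | 0.638 | 0.513 |

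The drops are 4.4 to 5.9, 9.3 to 12.4 and 14.7 to 19.1 percentage points. The plan's 80.1% comes from its own stratified two-stage simulation, whose inputs are not all given, so only the differences should be read from this table.

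**The case against.** The best defence is that Table 10 sets what is routinely reported, while 11.3.1 sets what is collected. On that reading a blank cell does not forbid recording, and both rules can be followed together. Much of this stands. A reader might infer that a site omitting an on-treatment Grade 2 case would still be within the protocol; it would not, because 11.3.1 requires all adverse events to be collected up to 30 days after treatment. What does not stand is that the split is clear. The documents never state it for the endpoint, and 11.3.1 sits under a heading about serious-event reporting to the drug supplier, where a site may not look for its general collection rule.

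Second, Unrelated or Unlikely is not the only natural score. The definition of Possible also allows for other therapy as the cause, and pneumonitis arising on blinded study drug can fit it. This stands: the gap opens only when the investigator chooses a lower score, and the documents do not show how often that would happen.

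Third, pneumonitis has its own evaluation in 9.5, with imaging support in note 6 to Table 5 ("HRCT chest alone will be sufficient whenever new onset of dyspnea occurs and radiation pneumonitis is suspected to have occurred"), and the case report forms may hold a dedicated endpoint item. The 9.5 visit is a real safeguard, and on its text it covers patients off study drug. But it depends on suspicion, and it does not say that its findings escape Table 10. The forms are not in the documents, so a dedicated item can be neither confirmed nor excluded.

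Fourth, a reader might infer a biased comparison. The documents do not support that. Assignment is masked, and the only reversal in the illustration removes two placebo events and no nintedanib events.

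**Conclusion.** The inconsistency is real, and its consequence is limited. Read literally, Table 10 lets a Grade 2 endpoint event go unreported when it is scored Unrelated or Unlikely. Sections 11.3.1 and 9.5 point the other way, and nothing ranks them. The Table 5 conflict is equally plain, but for the primary endpoint it reaches only patients whose last dose comes before about treatment day 97 to 125, and they keep the 9.5 visit.

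The plan does not give the share of events at Grade 2, their likely attribution or the early-stopping rate, so neither the size nor the direction of any loss can be derived. The p-values and power drops are illustrations under assumed losses. They show that with 16 to 17 expected events a small loss is not negligible; they do not show that one will occur. A reader might go further and infer that the primary endpoint goes uncollected or that the trial is biased, and the documents support neither. This is a cheap improvement.

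**What to change.** In 11.1.3, beside Table 10, state that radiation pneumonitis of Grade 2 or above is recorded and graded whatever its attribution, through six months after chemoradiation, for every randomised patient on or off study drug. Reconcile the Table 5 adverse-event row and the 11.1.3 time limit with 9.7 to 9.9, 11.3.1 and the synopsis.

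Two short clarifications would help: that the 9.5 evaluation continues to apply after study drug is stopped, since Table 5 groups that column under active treatment; and that follow-up under 7.5, which names only secondary endpoints for patients who start systemic therapy for progression, includes the primary endpoint, as intent-to-treat already implies.

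The cost is protocol wording and slightly more data entry for patients who stop early. No visit is added.
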